2.3 DETERMINATION OF SAMPLE SIZE

A sample size of approximately 80 patients was selected based on the AE discontinuation rates after one year observed in the randomized Phase 3 pirfenidone studies and the randomized Phase 2 and 3 nintedanib studies (pirfenidone 14.6% AE discontinuation [Esbriet® US label 2014]; nintedanib 21% AE discontinuation [Ofev® US label 2014]). Given that for pirfenidone the discontinuation rate after 24 weeks was 6%-8% in studies PIPF-004 and PIPF-006 it is a reasonable assumption that the nintedanib discontinuation rate was around 10%-11%. As in this study of combination treatment, it is possible that the addition of nintedanib to ongoing pirfenidone treatment could increase the proportion of patients who discontinue because of an AE, given the overlap in the GI and hepatic effects of pirfenidone and nintedanib.

Assuming 85% of the patients complete 24 weeks of combination treatment, a sample size of 80 patients would be expected to yield an actual completion rate of 77.2% - 92.8% using a 95% confidence interval (CI). [Table 1](#) shows the 95% CIs associated with projected completion rates of 75%, 80%, 85%, 90% or 95%, assuming an 80-patient sample size.

Table 1 Confidence Limits for Sample Size Determination

Number of Patients who completed 24 weeks	Proportion of Patients who completed 24 weeks	Lower Bound of 95% CI	Upper Bound of 95% CI
76	95.0%	90.2%	99.8%
72	90.0%	84.4%	96.6%
68	85.0%	77.2%	92.8%
64	80.0%	71.2%	88.8%
60	75.0%	65.5%	84.5%

CI = confidence interval

Patients who are withdrawn from the study will not be replaced.

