4.7.1 Treatment Completion/Early Discontinuation

A summary of the number and proportion of patients who complete 24 weeks of combination treatment (with 95% CI) will be presented. A patient is considered to have completed 24 weeks of combination treatment, if the eCRF question "Did the subject complete the treatment?" is ticked "Yes" (eCRF form "Study Drug Completion/Early Discontinuation"). It is expected that these patients have completed the Week 24 visit within expected time window (see Section 4.9).

The number and proportion of patients who complete 24 weeks of combination treatment (with 95% confidence interval (CI)) on pirfenidone at a dose of 1602-2403 mg/d and nintedanib at a dose of 200-300 mg/d will be presented. Average daily dose information as defined in Section 4.7.2 will be used to assess whether a patient completed 24 weeks on target dose.

The number and percentage of patients who discontinued combination treatment because of an adverse event (with 95% CI) will also be presented. This summary comprises patients who have reported "Adverse Event" as the main reason for treatment discontinuation.

The duration of combination treatment will be summarized descriptively. Duration of combination treatment will be defined as the time (days) from combination treatment start date (see Section 4.2.2) to the date subject completed or early discontinued from combination treatment period as per eCRF (Study Drug Completion/Early discontinuation form).

Kaplan-Meier (KM) plots for time to treatment discontinuation will be provided, based on the date subject completed or early discontinued from combination treatment period, as per eCRF (see Section 4.2.5).

Details on treatment and study discontinuations will be listed.

Logistic regression analysis will be used to assess the influence of baseline covariates on the discontinuation rate in an exploratory manner. The following parameters will be used to explain early treatment discontinuation:

- Age (years) at baseline,
- Sex (female = 0, male = 1),
- FVC % predicted at baseline,
- DLco % predicted at baseline.
- Region (US vs non-US)

Further parameters will be analyzed on an exploratory basis.

The regression coefficients for each covariate, together with the standard error and p-value will be presented. Further, odds ratios and 95% confidence intervals will also be given. In addition, a model including all covariates will be investigated in order to assess the consistency of the results.

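### The five-covariate discontinuation model has about 12 expected events, and the SAP sets no estimation method or sparse-data rule for it

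*SAP*

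**What the plan says.** Section 4.7.1 of SAP V2.0 states: "Logistic regression analysis will be used to assess the influence of baseline covariates on the discontinuation rate in an exploratory manner". It goes on: "The following parameters will be used to explain early treatment discontinuation", and lists age, sex, FVC % predicted, DLco % predicted and region (US or non-US). That makes five terms of one degree of freedom each. It also says "Further parameters will be analyzed on an exploratory basis", without giving a number.

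For each covariate the section promises the coefficient, standard error, p-value, odds ratio and 95% confidence interval. As an addition, "a model including all covariates will be investigated in order to assess the consistency of the results". No estimation method is named, and nothing is said about separation, non-convergence or few events. V1.0 has the same text, so the revision left this open.

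The expected number of events follows from Section 2.3: "Assuming 85% of the patients complete 24 weeks of combination treatment, a sample size of 80 patients" is the planning case, and Table 1 covers "projected completion rates of 75%, 80%, 85%, 90% or 95%, assuming an 80-patient sample size". Section 4 states that no formal hypothesis tests will be performed.

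**The concern.** Logistic regression with very few events per covariate has two known weaknesses under maximum likelihood. Slopes tend to be exaggerated when a true effect exists. The fit may also have no finite solution, for example when no woman, or nobody in one region, discontinues. The joint model here has about 2.4 events per covariate at the planning rate.

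Two things are at stake. If the joint fit fails, the planned table cannot be produced, and the remedy would be chosen after the data have been seen, in an open-label study. If it converges, the odds ratios may be somewhat too large, and comparison with the single-covariate fits carries a small artefact. Section 4.7 names early discontinuation among the endpoints of main interest, so its reported predictors will be read.

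**Working it through.** **1. The plan's own figure.** The interval in Section 2.3 is reproduced by p ± 1.96 × √(p(1 − p)/n), with p = 0.85 and n = 80: 0.85 ± 1.96 × √(0.1275/80) = 0.85 ± 0.078, that is 77.2% to 92.8%, as printed.

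**2. Expected events.** Events = 80 − completers; divide by 5 covariates.

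| Completion | Completers | Events | Events per covariate |
|---|---|---|---|
| 95% | 76 | 4 | 0.8 |
| 90% | 72 | 8 | 1.6 |
| 85% | 68 | 12 | 2.4 |
| 80% | 64 | 16 | 3.2 |
| 75% | 60 | 20 | 4.0 |

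Any further parameters added to the joint model would lower the last column.

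**3. Simulation set-up.** There were 2,000 trials per scenario with n = 80, each fitted by maximum likelihood and by Firth. The following assumptions are not in the SAP: three standardised continuous covariates with odds ratio 1.5 or 0.67 per SD; FVC–DLco correlation 0.4; 70% or 80% male; 50% US; sex odds ratio 2 or 0.5; region odds ratio 2; plus one scenario with no effects.

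**4. Maximum likelihood at about 12 events.** Bias is the percentage of the true log-odds ratio, among converged fits.

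| Scenario | Failed or separated | Bias, continuous covariates | Bias, region | Bias, sex |
|---|---|---|---|---|
| 80% male, sex OR 2 | 22.7% | +12% to +21% | +16% | −27% |
| 70% male, sex OR 2 | 10.8% | +16% to +22% | +11% | +4% |
| 80% male, sex OR 0.5 | 4.0% | +12% to +19% | +18% | +11% |
| 80% male, no effects | 9.2% | none | none | none |

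In the first row the region odds ratio averages 2.23 against a true 2, while sex averages 1.66 against a true 2. Sex shrinks because the separated samples, which carry the largest sex effects, drop out.

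**5. Failure over the tabulated completion rates** (80% male, sex OR 2): 70.7% at 4 events, 39.4% at 8, 22.7% at 12, 11.1% at 16 and 6.2% at 20.

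**6. Firth at about 12 events.** Every fit was finite.
- Region: mean log-odds ratio 0.69 to 0.70 against a true 0.69. RMSE was 0.72 to 0.76, against 0.82 to 0.87 for converged maximum-likelihood fits.
- Continuous covariates: 0.39 to 0.42 in absolute value, against a true 0.41.
- Sex: 0.63 against 0.69 with 80% male and OR 2, close to the truth in the other scenarios. Its RMSE was not uniformly lower (0.95 over all Firth fits against 0.87 over converged maximum-likelihood fits in the first scenario).
- Interval width (upper limit divided by lower limit of the odds ratio): about 15 for region (maximum likelihood 18 to 19) and 22 to 42 for sex (28 to 53).
- Mean predicted discontinuation: 17.0% against 15.0% observed.

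**7. Firth at about 4 events.** Mean sex log-odds ratio was 0.21 against 0.69, and mean predicted discontinuation 7.8% against 5.1%.

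**8. Joint against single-covariate fits.** In a separate simulation (2,000 trials, about 12 events, true region OR 2), the joint maximum-likelihood model failed in 5.7% of trials and the region-only model in 1.3%. With no effect of the other four covariates, the region log-odds ratio averaged 0.789 in the joint fit and 0.739 alone (true 0.693), a gap of 0.050. Under Firth the gap was −0.001.

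**The case against.** The strongest reply is that this is an add-on to an exploratory analysis, without formal tests, where bias is small beside noise. In the first scenario the region bias is 0.155 × 0.693 = 0.108; squared, 0.0116, against a mean squared error of 0.82² = 0.672, or about 1.7%. Wald coverage among converged maximum-likelihood fits was 95% to 97%. The joint fit stays imprecise under either method. All of this stands, and it caps the severity.

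A reader might also infer more than the SAP supports:

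- *That the plan prescribes ordinary maximum likelihood.* It does not. That is the usual software default; the defect is an unspecified method.
- *That the full set of outputs is promised from the joint model.* The outputs are listed for each covariate before the joint model is introduced, and its own outputs are not listed.
- *That all odds ratios will be inflated.* There was no systematic inflation without true effects, and sex can move toward the null.
- *That the joint model will contradict the single fits for purely numerical reasons.* The gap of 0.050 is real but smaller than the random scatter between the fits. Correlated covariates and non-collapsibility of the odds ratio also separate them, and Firth removes neither.
- *That Firth solves everything at no cost.* It pulls predicted probabilities toward 1/2, leaves intervals wide and does not rescue a model with about 4 events.

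What survives is the failure rate, the conditional bias and the missing rule. Dropping covariates would be a reasonable alternative, but would change the model that the plan commits to.

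**Conclusion.** The point holds as a low-severity gap. The SAP commits to a five-covariate logistic model with about 12 expected events (2.4 per covariate; 0.8 to 4.0 over its own range) and sets neither a method nor a sparse-data rule. Under default maximum likelihood at about 12 events, the joint fit would separate or fail in roughly 4% to 23% of trials. Among converged fits, non-null region and continuous-covariate log-odds ratios would be about 11% to 22% too far from zero.

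The event count rests on the 85% planning assumption. The failure and bias figures rest on covariate distributions and effect sizes that the SAP does not give, so they show a plausible range and do not predict this trial. The primary outcome is not affected.

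**What to change.** Add to Section 4.7.1:

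*The all-covariate logistic model, and for comparability the single-covariate models, will be fitted by Firth's penalised likelihood with profile penalised-likelihood 95% CIs. The number of events will be shown beside each model, and the consistency check will be read in light of its limited precision.*

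The cost is one model option in standard software and slightly smaller estimates. The pull of predicted probabilities toward 1/2 matters little, because the section lists odds ratios and no predicted probabilities; if probabilities are ever reported, an intercept correction should be added. If the event count comes out near 4, the joint model should be described as uninformative whichever estimator is used.

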4.7.2 Exposure of Study Medication

Summaries of dosing, treatment duration, dose interruptions or reductions will be provided for each treatment separately, as well as for combination treatment, if applicable.

Generally, treatments administered from combination treatment start date up to the 'Date subject completed or early discontinued from combination treatment period' as per eCRF 'Study drug completion/Early Discontinuation' will be considered for exposure analyses. All drug records before or after these dates reported in the drug-log will be disregarded. The below definitions are to be interpreted within this time window.

The overall **treatment duration** (weeks), including and excluding dose interruptions, will be summarized descriptively. Also the days with dose interruptions will be given in this presentation.

The overall treatment duration **including** dose interruptions will be defined as follows:

- Overall duration of combination treatment including dose interruptions = [(Date of discontinuation/completion of combination treatment – date of initiation of combination treatment) + 1]/7.

The date of first administration of nintedanib and pirfenidone on or after the Baseline visit will be considered as initiation date of combination treatment (see Section 4.2.1).

- Overall treatment duration of pirfenidone or nintedanib alone including dose interruptions = [(Date of last non-zero dose of treatment received until

**Pirfenidone and nintedanib — F. Hoffmann-La Roche Ltd
Statistical Analysis Plan MA29895, Version 2.0, final, 17 May 2017**

discontinuation/completion of combination treatment – date of initiation of combination treatment) + 1]/7.

The overall treatment duration **excluding** dose interruptions will be derived from the treatment administration panels, considering only days on treatment. When calculating duration of combination treatment, only days where both, pirfenidone and nintedanib, were interrupted will be excluded.

Dose interruptions will be calculated by summing all days where dose (pirfenidone or nintedanib) was interrupted. Combination treatment will only be considered to be interrupted if both, pirfenidone and nintedanib, were interrupted.

The total number of patient days on treatment, including and excluding dose interruptions, and the total number of patient days with dose interruptions, will be presented.

The **total dose** (mg), the **last dose administered** (mg/d) and the **average daily dose** for each of the study treatments will be presented descriptively. The average daily dose will be calculated by summing up the number of capsules taken during the combination treatment period, divided by the number of days on combination treatment including treatment interruptions, as defined above. Further, frequencies for categories of average daily doses (e.g. <1602, 1602 – 2403, >2403 mg/d for pirfenidone, and <200, 200 – 300, >300 for nintedanib, as well as combinations of both) will be presented.

Dose modifications and dose interruptions will be analyzed for any dose modification or dose interruption, as well as for dose modifications and drug interruptions separately. Numbers and proportions of patients with at least one dose modification or dose interruption will be presented for each treatment separately. Numbers and proportions of patients with 1, 2, 3 or more dose modifications or drug interruptions will be given.

Numbers and frequencies of reasons for dose modification or dose interruption will be presented.

Analyses will be based on the information on dose modifications or dose interruptions as provided by the investigator on the eCRF study drug administration page for data collected between the time of start of combination treatment and discontinuation/completion of combination treatment.

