2. STUDY DESIGN

This is a multicenter, international, open-label, single-arm safety and tolerability study of pirfenidone/nintedanib combination treatment in patients with IPF who have been on a stable dose of pirfenidone with demonstrated tolerability. In this study, a stable pirfenidone dose will be defined as 1602–2403 mg/d (801 mg twice daily [BID] or three times daily [TID]). Up to approximately 60 clinical centers in the US, Europe, and Canada are expected to enroll up to approximately 80 patients. Patients who are withdrawn from the study will not be replaced.

At the start of Screening, patients will have been on pirfenidone for at least 16 weeks and on a stable dose (1602–2403 mg/d) for at least 28 days; also, the dose must be expected to remain within that range throughout the study. In addition, in the 28 days before the start of Screening, patients must not have experienced either a new or
Pirfenidone and nintedanib — F. Hoffmann-La Roche Ltd
Statistical Analysis Plan MA29895, Version 2.0, final, 17 May 2017

ongoing moderate or severe adverse reaction considered by the Investigator to be related to pirfenidone, or an interruption of pirfenidone treatment for > 7 days for any reason.

2.1 **PROTOCOL SYNOPSIS**

The Protocol Synopsis is in [Appendix 1](#). For additional details, see the Schedule of Assessments in [Appendix 2](#). For additional details, please see the Protocol Amendment Version 3, 21 June 2016 (and its Appendices).

2.2 **OUTCOME MEASURES**

The primary objective for this study is to investigate the safety and tolerability of adding nintedanib to treatment with pirfenidone in patients with IPF. Consequently, the primary objectives of this study focus on safety and tolerability and not efficacy.

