2.2.5 Safety Outcome Measures

The primary safety outcome measure is:

- Proportion of patients who complete 24 weeks of combination treatment on pirfenidone at a dose of 1602–2403 mg/d and nintedanib at a dose of 200–300 mg/d.

Secondary safety outcome measures are:

- Proportion of patients who discontinue pirfenidone, nintedanib, or both study treatments because of adverse events before the Week 24 visit,
- Total number of patient days of combination treatment with pirfenidone at a dose of 1602–2403 mg/d and nintedanib at a dose of 200–300 mg/d,
- Total number of days from the initiation of combination treatment to discontinuation of pirfenidone, nintedanib, or both study treatments,
- Frequency and timing of Adverse Events (AEs) and Serious Adverse Events (SAEs).

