An independent Data Monitoring Committee (iDMC) will review safety data and advise on study conduct at least three times during the study: when the first approximately 20 patients have completed 8 weeks of combination treatment or permanently discontinued study treatments, when approximately 50% of the total patient group has completed 12 weeks of combination treatment or permanently discontinued study treatments and when approximately 75% of the total patient group has completed 24 weeks of combination treatment or permanently discontinued study treatments. Additional ad hoc meetings or data reviews can be requested at any time by the iDMC or the Sponsor, if warranted.

Design of Study

NUMBER OF PATIENTS

Number of patients to be enrolled: approximately 80

TARGET POPULATION

Inclusion Criteria

Eligible patients for this study must meet the following criteria for study entry:

1. Written informed consent to participate in the study
2. Male or female, and age 40 through 80 years old at the start of Screening (inclusive).
3. At the start of Screening, on pirfenidone for at least 16 weeks and on a stable dose for at least 28 days (in this study, a stable dose will be defined as 1602-2403 mg/d); the dose must be expected to remain in that range throughout the study.
4. Documented diagnosis of IPF, per the Investigator per using the criteria of the 2011 American Thoracic Society / European Respiratory Society / Japanese Respiratory Society / Latin American Thoracic Association guidelines
5. The value from pulmonary function test results (from documented pulmonary function laboratory reports) measured at the screening visit as follows:
 - Percent predicted FVC ≥ 50%.
 - Percent predicted DLco (or carbon monoxide transfer capacity converted to DLco) ≥ 30%
6. Able to understand the importance of adherence to the study treatment regimen and the study protocol, and willing to follow all study requirements, including the concomitant medication restrictions, throughout the study.
7. For women of childbearing potential: agreement to remain abstinent (refrain from heterosexual intercourse) or use two adequate methods of contraception, including at

Pirfenidone and nintedanib — F. Hoffmann-La Roche Ltd
Statistical Analysis Plan MA29895, Version 2.0, final, 17 May 2017

41

least one method with a failure rate of < 1% per year, during the treatment period and for at least 3 months after the final Follow-up Visit.

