Note: the following are permitted: prophylactic low-dose heparin or heparin flush as needed for maintaining an indwelling intravenous device (e.g., enoxaparin 4000 IU SC per day), as well as prophylactic use of antiplatelet therapy (e.g., acetylsalicylic acid up to 325 mg/d, clopidogrel at 75 mg/d, or equivalent doses of other antiplatelet therapy).

15. Use of strong CYP1A2 inhibitors (e.g., fluvoxamine, enoxacin) in the 28 days before the start of Screening.
16. Use of inhibitors of P-glycoprotein (e.g., ketoconazole, erythromycin) or CYP3A4 (e.g., ketoconazole, erythromycin) or their inducers (e.g., rifampicin, carbamazepine, phenytoin, St John’s wort) in the 28 days before the start of Screening.
17. History of alcohol or substance abuse in the 2 years before the start of Screening.
18. Use of any tobacco product in the 12 weeks before the start of Screening, or an unwillingness to abstain from their use through the final Follow-up Visit.
19. In the judgment of the Investigator, not a suitable candidate for enrollment, or unlikely or unable to comply with the requirements of this study.
20. Use of any investigational therapy in a clinical study protocol in the 28 days before the start of Screening
21. Pregnancy or lactation.
22. Hypersensitivity to peanuts.
23. Hypersensitivity to soy.

END OF STUDY AND LENGTH OF STUDY

Length of Study

The expected study length is up to 21 months

End of Study

January 2018

**Pirfenidone and nintedanib — F. Hoffmann-La Roche Ltd
Statistical Analysis Plan MA29895, Version 2.0, final, 17 May 2017**

INVESTIGATIONAL MEDICINAL PRODUCTS

PIRFENIDONE

Pirfenidone is approved in a 267 mg capsule dosage form.

The recommended dose is 801 mg (i.e., three 267 mg capsules) TID, at the same times each day, taken with food (total dose, 2403 mg/d). At the beginning of the study, patients will be on a stable pirfenidone dose, as defined in the inclusion criteria.

NINTEDANIB

Nintedanib is approved in 100 mg and 150 mg capsule dosage forms.

The recommended dose is 150 mg BID, approximately 12 hours apart, at the same times each day, taken with food (total dose, 300 mg/d). Both 100 mg and 150 mg capsules will be supplied to facilitate temporary dose reduction if required to manage AEs.

STATISTICAL METHODS

PRIMARY ANALYSIS

The analysis population will be the Safety Population. It will consist of all patients who received at least one dose of nintedanib or pirfenidone at the Baseline Visit (Day 1).

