- Patients taking prohibited medications enter Washout; if prohibited medication must be tapered, patient must be off that medication 28 days before start of Screening. Other patients directly enter Screening.
- For patients who complete 24 weeks of study treatment, visit should occur 28–35 days after completion of combination treatment. For patients who prematurely discontinue study treatment or have a treatment interruption of ≥ 28 consecutive days, visit should occur 28–35 days after decision to discontinue nintedanib.
- If a patient cannot return in ≤ 7 days, study center is to call patient to review medical history and to send laboratory kit and shipping supplies to patient so that blood samples can be drawn at another study center, commercial laboratory or by home nursing agency; Early Discontinuation Visit should then be scheduled as soon as possible.
- Written informed consent must be obtained before any study-mandated assessment or procedure, including tapering and/or discontinuing prohibited medication. If written informed consent was not obtained at Washout, it must be obtained at start of Screening.
- Including systems review, and review of concomitant medications, events in 28 days before start of Screening, and historical data (including prior high-resolution computed tomography scans, pulmonary function tests, and surgical lung biopsy data, if available). If complete medical

Pirfenidone and nintedanib — F. Hoffmann-La Roche Ltd
Statistical Analysis Plan MA29895, Version 2.0, final, 17 May 2017

history was obtained during Washout, during Screening the list of concomitant medications and medical history should be updated with changes since patient signed informed consent form.

- f. Includes AEs, concomitant medications, dosing adherence, hospitalizations, inquiry regarding compliance with protocol requirements for contraceptive use and avoiding tobacco products, and inquiry regarding whether patient is aware of being pregnant.
- g. At start of Screening, patient must have been on pirfenidone for ≥ 16 weeks and on stable dose (1602–2403 mg/d) for ≥ 28 days; dose must be expected to remain in that range throughout study. Treatment interruptions > 7 days are not permitted in the 28 days before start of Screening.
- h. At Baseline Visit, patient must have been at least approximately 80% adherent to pirfenidone dosing regimen since Screening Visit.
- i. Resting BP and HR, respiratory rate, body temperature.

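### The pirfenidone floor in the primary outcome equals an admitted entry dose, so a patient who stays at 1602 mg/d is scored off target after one logged missed capsule

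*SAP*

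**What the plan says.** All references are to SAP V2.0 unless stated.

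- **Outcome.** Section 2.2.5 gives the primary measure as "Proportion of patients who complete 24 weeks of combination treatment on pirfenidone at a dose of 1602–2403 mg/d", together with nintedanib at 200–300 mg/d.
- **Scoring rule.** Section 4.7.1: "Average daily dose information as defined in Section 4.7.2 will be used to assess whether a patient completed 24 weeks on target dose".
- **Average.** Section 4.7.2 obtains it by "summing up the number of capsules taken during the combination treatment period, divided by the number of days on combination treatment including treatment interruptions". Its duration formula counts both the first and the last day, and drug-log records outside that window are ignored.
- **Limits.** Section 4.7.2 gives example categories "<1602, 1602 – 2403, >2403 mg/d for pirfenidone", so 1602 itself is on target and anything below is not. No rounding rule or tolerance follows.
- **Entry doses.** Section 2: "a stable pirfenidone dose will be defined as 1602–2403 mg/d (801 mg twice daily [BID] or three times daily [TID". Inclusion criterion 3 in Appendix 1 repeats that "a stable dose will be defined as 1602-2403 mg/d" and requires only that the dose be expected to remain in that range.
- **Capsules.** Appendix 1: "The recommended dose is 801 mg (i.e., three 267 mg capsules) TID".

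Section 4.7.2 of V1.0 uses the same average-dose rule, so this did not arise with V2.0.

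**The concern.** The outcome is worded as a dose level. The scoring rule turns it into an average of actual intake, measured against one absolute floor. That floor coincides with one of the two regimens named at entry. For a patient held at that regimen, average intake can equal the floor but cannot exceed it, so any logged shortfall, however small and whatever its cause, counts as failure.

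A patient at the upper regimen has a wide margin under the same rule. Two patients who tolerate the combination equally well can therefore be classified differently in the primary outcome because of the dose at which they entered. In addition, the rule sums capsules while the limits are in mg/d, so an unstated choice of unit or rounding can decide the result for a patient at the boundary.

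**Working it through.** **Inputs.** Capsule strength 267 mg, three capsules per 801 mg dose (Appendix 1). Limits 1602 and 2403 mg/d (Sections 2.2.5 and 4.7.2). Duration 24 weeks = 168 days; the ±7-day visit window in Appendix 2 gives 161 to 175.

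**The plan's own limits.** BID: 2 × 3 × 267 = 1602 mg/d. TID: 3 × 3 × 267 = 2403 mg/d. Both reproduce.

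**Formula.** Average daily dose = capsules taken × 267 / days, with days = end date − start date + 1.

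**Patient who stays at 801 mg BID, 168 days** (6 × 168 = 1008 capsules):
- Full intake: 1008 × 267 / 168 = 1602.00, on target with zero margin.
- One missed capsule: 1007 × 267 / 168 = 1600.41, off target. At 161 and 175 days the values are 1600.34 and 1600.47, also off target.
- One 801 mg dose unlogged on a partial first or last day that the denominator still counts: 1005 × 267 / 168 = 1597.23, off target.

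**Patient who stays at 801 mg TID, 168 days** (9 × 168 = 1512 capsules):
- 504 missed capsules (504 / 1512 = 33.3%): 1008 × 267 / 168 = 1602.00, on target.
- 505 missed capsules: 1600.41, off target.

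**Margin by constant dose**, 1 − 6 / (capsules per day): 0% at 1602, 14.3% at 1869, 25% at 2136, 33.3% at 2403 mg/d.

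**Rounding.** After one missed capsule the BID patient averages 1007 / 168 = 5.994 capsules per day. Rounded to one decimal this is 6.0, which converts to 1602 and is on target. Rounded in whole mg it is 1600 and off target. The SAP does not say which applies.

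**Effect on the primary proportion.** The documents do not give the share entering at 1602 mg/d. With 80 patients, each patient who would otherwise qualify and is lost to this rule lowers the proportion by 1 / 80 = 1.25 percentage points. As an assumption, if 5%, 10%, 20% or 30% of patients (4, 8, 16 or 24) stay at 1602 mg/d, the loss lies between zero and 5, 10, 20 or 30 points. The upper end needs every one of them to qualify otherwise and to have at least one logged miss.

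**The case against.** The case on the other side narrows the point but does not remove it.

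- **Entry dose is not fixed.** A reader might infer that patients are expected to stay at their entry regimen, so that every BID patient fails and every TID patient passes. Criterion 3 speaks only of the range. A patient who later takes more within it gains margin, and intermediate doses already have some. The zero margin applies to patients who remain at 1602 mg/d.
- **The log may not record single capsules.** Appendix 1 places daily adherence in the patient diary, whereas exposure is derived from the drug log. If the log holds only periods at a recorded dose, a BID patient with no recorded interruption averages exactly 1602 and passes. The SAP does not settle this.
- **The width at 2403 mg/d is partly intended.** The outcome is an absolute range, so a patient reduced to 1602 mg/d is meant to count as on target. Interruption days and counts are also tabulated separately in Section 4.7.2. The TID margin is a contrast here, not a defect in itself.
- **The 85% is not a benchmark.** It is tempting to set a lowered primary proportion against the 85% of Section 2.3. That figure is completion without any dose condition, and Section 4.7.1 reports that proportion separately from the eCRF completion question.
- **The 80% is not an analysis standard.** Footnote h of Appendix 2 says that the "patient must have been at least approximately 80% adherent to pirfenidone dosing regimen since Screening Visit". That is an eligibility check over a screening period of at most 21 days.
- **Regimen is not shown to dominate.** A reader might infer that the primary result depends mainly on entry regimen. It also requires the completion tick and the nintedanib range, and the BID share is unknown.

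Nothing in the document supplies the missing tolerance or rounding rule, so the boundary problem stands.

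**Conclusion.** The rule is wrong as written at its lower bound. It has no margin for a patient who stays at an admitted dose, so it can score full tolerability as failure on a single capsule in 1008 or on how a part-day is logged.

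This rests on three conditions: the patient remains at 1602 mg/d, the drug log captures the missed intake, and the limit is applied to the unrounded mg/d value (or that value rounded to whole mg). The effect on the primary proportion cannot be stated, because neither the share at 1602 mg/d nor the log's level of detail is given.

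The point should be fixed but is not critical. The study is single-arm and descriptive, with no hypothesis test and no stated success threshold, so no formal decision turns on this proportion.

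**What to change.** Before database lock, state in Section 4.7.1 how the pirfenidone dose condition is decided, by one of two routes:

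1. from the dose level that the investigator recorded in the drug log; or
2. from the average daily dose, with a pre-specified tolerance at the lower bound, a stated unit and a rounding rule.

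Either route should ensure that trivial missed intake at an admitted dose does not count as failure. Keep the present capsule-average version as a supportive analysis. Show the primary result and interruption days by pirfenidone regimen at Day 1. The subgroup list in Section 4.5.6 is redacted, so this display may already be planned. If a relative-intake condition is also wanted, the sponsor should fix the fraction in advance.

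No dose or clinical rule changes. The cost is SAP wording and one extra derivation from data already collected, and some patients near the lower bound will change category.
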